sensitive and specific to progression or improvement in clinical status of the patient. We will therefore correlate scores on the Comorbidity Index, Kubo INPH Scale, Kiefer's index domains for gait/balance, headache and dizziness, European NPH Scale, INPH Diagnosis Checklist with the Black Outcome Scale, Marmarou Recovery Scale, modified Rankin scale, Barthel index. Furthermore, we would test the hypothesis of association of NPH with congenital hydrocephalus or early childhood changes in brain (long standing overt ventriculomegaly) which may manifest as large heads. We will correlate head circumference at baseline and with outcomes at various time points.

4. Study Procedures

[figure not shown]
a. Study design, including the sequence and timing of study procedures (Distinguish research procedures from those that are part of routine care).

Page 4 of 11

Principal Investigator: [name]

Application Number: NA_00042178

Follow-up at 6, 12, 18, 24 months for long-term response rates

The study is a randomized 2x2 double-blinded cross-over design study with two armscomparing optimally functioning shunts (Optimal drainage) to the placebo treatment wherein there is minimal CSF flow through the shunts (sub-optimal drainage). The state of sub-optimal drainage of shunt will be attained by raising the opening pressure of the shunt valve to maximum which will impede the CSF flow. All patients who are candidates for shunt surgery based upon standard of care practice of CSF drainage trial will enter the study. Only patients who are not at significant risk of falls will be included in the study i.e patients with Tinetti score >18. Furthermore, the neurosurgeon/neurologist will not be blinded to patients shunt valve status. Only the nurse practioner or physiotherapist performing the study evaluation would be blinded. All evaluation data would be made available to neurologist/ neurosurgeon remain informed about treatment failure (Tinetti Gait and evaluation <18).

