During the initial phase of the study, participants will be randomized in 1:1 allocation ratio to optimally and sub-optimally draining shunt arms. After completion of six weeks the opening pressures for patients in the optimally draining shunt arm will be raised to minimize CSF flow (crossover to sub-optimally draining arm). Likewise, at 6 weeks patients initially in suboptimal drainage arm will have the opening pressures appropriately reduced so that flow through the shunt is optimal (crossover to optimal drainage shunt arm). X-rays will be performed to confirm shunt valve settings. Since the shunt is only effective during the time it is effectively draining and the carryover effect is minimal (i.e., often lasting for no more than a few days), there will be no washout period between arms. Patients will undergo every third week evaluations regardless of the study arm to evaluate safety as well as efficacy. Patients and the psychometrician, physical therapist and nurse practitioner who assess the outcome measures will be blinded to the shunt status. Only the study neurosurgeon and neurologist will be aware of the shunt status, and will make clinical (safety) decisions after being informed of Tinetti gait and balance scores. The follow-up and evaluation timeline is indicated in the algorithm above. The Neurosurgeon will be notified about the gait and balances score and will make a clinical (safety) decision accordingly. Any patient whose gait deteriorates to Tinetti < 18 or has a fall will be regarded as a treatment failure. Patients who are a treatment failure during the

Principal Investigator: [name]

Application Number: NA 00042178

suboptimal drainage arm will have the opening pressure of the valve adjusted. These patients would then be considered to be crossed over to draining arm if they were in the initial suboptimal drainage arm of the study. If a patient who has already been crossed over from optimally draining shunt to sub-optimally draining shunt arm worsens, s/he will have the shunt pressure turned down and will be followed according to standard of care protocol at 6 monthly intervals. During this time, we will collect data on these follow-up visits as part of the research.

Standard of care procedures: Shunt surgery, Post op evaluations while shunt is in optimal drainage setting, 6, 12 months, 18 months and 24 months post-op visit

Research procedures: Visits during non-draining shunt period

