b. Study duration and number of study visits required of research participants.

The study duration and number of visits for each participant will vary depending on the arm of the study the patient enters first (flow chart above).

Non-Draining → Draining Shunt arm

Baseline preoperative visit → Shunt surgery → Sub-optimally draining shunt → first visit within 2 weeks from surgery 6 weeks visit, → cross over to draining Shunt arm at 6 week visit along with x-rays confirmation of the new valve settings → 9 weeks visit → 12 weeks visit Total duration 12 weeks from shunt surgery

Number of total Visits=4

Draining → Non-Draining Shunt arm

Baseline preoperative visit → Shunt surgery → Draining shunt → first visit within 2 weeks from first surgery →, 6 weeks visit, → cross over to non-draining Shunt arm at 6 week visit along with x-rays confirmation of the new valve settings → 9 weeks visit → 12 weeks visit Total duration 12 weeks from shunt surgery

Number of total Visits=4

- c. Blinding, including justification for blinding or not blinding the trial, if applicable.

 Patients and raters will be blinded to treatment status to minimize reporting bias. Neurologist and neurosurgeons will not be blinded for safety reasons.
- d. Justification of why participants will not receive routine care or will have current therapy stopped.

The study is designed to compare efficacy of shunt in comparison to sham/placebo (non draining shunt). Though shunt is standard of care it has not been systematically evaluated in a randomized trial. The length of time that a patient will have a non-draining shunt has been limited to 6 weeks and will be shortened if the patient shows a worsening in gait while on that arm.

e. Justification for inclusion of a placebo or non-treatment group.

The placebo arm is included to take into account any placebo effect. Current standard of care treatment of normal pressure hydrocephalus has not been evaluated in a placebo controlled trial. Current guidelines are based on studies which lack a comparison with placebo and their

Principal Investigator: [name]

Application Number: NA 00042178

outcomes have been highly variable. Thus a placebo control is needed to evaluate efficacy of shunt and to improve our selection criteria for shunt insertion.

f. Definition of treatment failure or participant removal criteria.

Failure: Any participant whose gait deteriorates to Tinetti≤18 will be considered a

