treatment failure as this is considered under standard of care to be high risk of fall.
Additionally any patient falling due to inability to balance or poor gait would also be
considered a treatment failure.

Any patient deteriorating to failure level or having a fall attributable to gait impairment will be recorded as a treatment failure for that arm of the study and if on suboptimal drainage arm will be crossed over to optimal drainage level.

Patients who fail would however continue to participate in study and data will be collected at all subsequent follow-up points regardless of the study arm as described above. Furthermore, for concerns of patient safety no patient who fails (Tinetti \leq 18) will subsequently have suboptimal drainage in shunt at anytime^{12,13}.

Response:

Gait

- Tinetti gait and balance scale: Measured with respect to baseline (pre-drainage trial scores)
- 2. TUG: Measured with respect to baseline (pre-drainage trial scores)
- 3. MCV Gait Grade: Measured with respect to baseline (pre-drainage trial scores)

Cognition

- 1. Mini Mental State Examination (MMSE)
- 2. Rey Auditory Verbal Learning Test (RAVLT): Measured with respect to baseline (pre-drainage trial scores)
- 3. Trail Making Test A & B: Measured with respect to baseline (pre-drainage trial scores)
- 4. Writing the Alphabet: Measured with respect to baseline (pre-drainage trial scores)
- 5. Beck Depression Inventory

Principal Investigator: [name]

Application Number: NA 00042178

- 6. Stroop test
- 7. Pegboard

Urinary

- 1. Urinary Incontinence Questionnaire (ICIq-UI): Measured with respect to baseline (predrainage trial scores)
- 2. Overactive Bladder Questionnaire (ICIq-OAB): Measured with respect to baseline (predrainage trial scores)
- 3. Quality-of-Life related to lower urinary tract symptoms (**ICIq-LUTSqol**): Measured with respect to baseline (pre-drainage trial scores)
- 4. Global quality-of-life assessment (**AUASSqol**): Measured with respect to baseline (predrainage trial scores)
- 5. Voiding Diary

Functional Scales

- 1. Barthel Index: measured with respect to baseline (pre-drainage trial scores)
- 2. Modified Rankin Scale
- g. Description of what happens to participants receiving therapy when study ends or if a participant's participation in the study ends prematurely.
- Inclusion/Exclusion Criteria3.1 Inclusion Criteria

 - Age of Patients (between 55 to 85 years old)
 - Clinically suspected iNPH with at least gait impairment.

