Though we do not expect any carryover effects, we will first test for period effects and treatment-period interactions by testing whether the magnitudes of the mean period differences are unequal and whether the overall means for each treatment order group are different. General linear models will be used to assess treatment effect while accounting for within patient correlation. F-tests (or non-parametric Wilcoxon rank sum tests if normality cannot be achieved) will be used to test significance of treatment effects.

Specifically for the primary outcome:

We will calculate the within patient difference in the Tinetti gait score, the MCV Gait Grade and the gait velocity at 6 weeks (end of first treatment period) and at 12 weeks (end of second treatment period). This difference is the same as it would be if we calculated the change from baseline at each time period. General linear model analysis will be employed to test for period and treatment effects and the interaction, while accounting for within patient correlation. If there is no period effect, then the analysis can be simplified to reporting a paired t-test of the difference in the Tinetti gait score, the MCV Gait Grade and the gait velocity between the optimal and sub-suboptimal 6-week follow-up. If any patient is a treatment failure and is discontinued from a treatment arm, the measure at the time of failure will be carried forward to the 6-week measure.

Sample size calculation:

A mean difference in the Tinetti score of 5 points would be considered clinically meaningful. Given the inclusion criteria of a baseline Tinetti score of >18 and data from our clinic, we estimate the standard deviation for the change to be 5 points. Using a two-sided t-test with the Type I error level of 0.05, we will have 80% power to reject the null hypothesis of no difference when the total sample size of a 2x2 crossover design is 34. Adjusting for a dropout rate of 20% a sample size of 42 study subjects would be required.

Principal Investigator: [name]

Application Number: NA 00042178

1. Boon, A., et al. Dutch normal-pressure hydrocephalus study: prediction of outcome after shunting by resistance to outflow of cerebrospinal fluid. *J Neurosurg* **87**, 687-693 (1997).

- 2. McGirt, M., et al. Diagnosis, treatment, and analysis of long-term outcomes in idiopathic normal-pressure hydrocephalus. *Neurosurgery* **62 Suppl 2**, 670-677 (2008).

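### Read literally, section 7c carries failure scores forward only from the non-draining arm, and no rule places a draining-first failure in the crossover difference; both gaps can raise the false-positive rate.

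*Combined protocol and SAP*

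**What the plan says.** **Carry-forward.** In section 7c, under the primary outcome, a failing patient who "is discontinued from a treatment arm, the measure at the time of failure will be carried forward to the 6-week measure". The rule therefore has two conditions: failure, and removal from an arm.

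**Who is removed from an arm.** Section 4f states that a failure "will be recorded as a treatment failure for that arm of the study". It then gives the only change of setting at failure, which is that the patient "if on suboptimal drainage arm will be crossed over to optimal drainage level". Section 4d says that time with a non-draining shunt "will be shortened if the patient shows a worsening in gait while on that arm". No section removes a draining failure from the draining arm. Failures "continue to participate in study and data will be collected at all subsequent follow-up points" (section 4f).

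**After failure.** Section 4f adds that no patient who fails on the Tinetti score "will subsequently have suboptimal drainage in shunt at anytime". Section 4a says that at six weeks "the opening pressures for patients in the optimally draining shunt arm will be raised to minimize CSF flow", with no exception for failures.

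**Analysis.** Section 7c takes the within-patient difference between weeks 6 and 12, fits a general linear model that allows for within-patient correlation, and permits a paired t-test if there is no period effect. It does not say whether the model is fitted to the differences or to all period scores.

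**The concern.** Two separate gaps follow from these passages.

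1. On the literal wording, the two arms are scored by different rules. A patient who dips below the threshold at an early check while non-draining is fixed at that score. A patient who dips while draining is scored at the scheduled visit, after any recovery. If low scores are partly transient, this creates a difference in favour of the shunt when none exists.
2. A draining-first Tinetti failure never receives the non-draining period and so has no score for it. If the pair is dropped, failures leave one sequence only. This gap remains even if carry-forward was meant for both arms.

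The trial was designed to separate a shunt effect from a placebo effect, so control of false positives is central. Without a written rule, the handling could also be chosen after the data are seen.

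**Working it through.** **The plan's own figure.** Section 7c uses a difference of 5, an SD of 5, two-sided 0.05 and 80% power. The standardised difference is 5/5 = 1. An exact two-sample t-test gives power 0.781 with 16 per group and 0.807 with 17, so the total is 34, as stated. Dropout: 34/0.8 = 42.5 against the stated 42, and 42 × 0.8 = 33.6. The evaluable number is therefore about 34, and 42 is the upper limit.

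**Mechanism, with no shunt effect.** The crossover estimate is half the sum of the two sequence means of (draining minus non-draining).
- In the non-draining-first sequence, literal carry-forward adds p × r. Here p is the chance of failing at an early check, and r is the mean recovery from the failure score to a later scheduled score.
- In the draining-first sequence, the second (non-draining) period adds a term of the same form and sign.
- Dropping draining-first failures keeps only patients whose first-period scores stayed above the threshold, which raises the draining mean in that sequence.
- If the same scoring rule applies to both periods and everyone is kept, the two sequences have the same distribution by randomisation. The period-adjusted contrast then has expectation zero.

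**Assumptions for size.** The documents give no failure rate or visit SD. Assumed: Tinetti only, latent level uniform 17 to 28, observed entry score at least 19, cap 28, failure at ≤18, visits at weeks 2, 6, 9 and 12, deviations independent between visits. Visit SD: if the whole SD of 5 for the change is visit noise, it is 5/√2 = 3.54 (the extreme). If a quarter of the variance is, it is √(0.25 × 12.5) = 1.77. The test is the period-adjusted two-sample test on differences.

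**Simulated two-sided error, visit SD 1.77 to 3.54:**

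| Handling | 34 patients | 42 patients |
|---|---|---|
| Literal carry-forward, pairs dropped | about 7% to 16% | about 8% to 20% |
| Literal carry-forward, week 12 by sequence | about 6% to 9% | about 6% to 10% |
| Equal carry-forward, all by sequence | about 5% | about 5% |

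**Separating the two gaps** (42 patients, visit SD 1.5 to 3.5, 12.2% to 25.5% failing in period 1). With pairs dropped, error is 6.9% to 18.4% under literal carry-forward and still 5.7% to 9.5% under equal carry-forward. Bias is 0.14 to 0.82 points and 0.08 to 0.51 points respectively. A mixed model on all period scores gives 5.8% to 9.0% under literal and 5.1% to 5.3% under equal carry-forward.

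**Sensitivity**
- Failure at <18 (42 patients, literal carry-forward): 5.6% to 14.2% with pairs dropped, 5.3% to 8.7% by sequence.
- Different assumptions (mean 23, between-patient SD 2.5, visit SD 3.54, checks at weeks 3, 6, 9 and 12): with pairs dropped, 15.8% for 34 patients and 19.2% for 42; by sequence, 8.7% and 10.0%. Equal carry-forward with everyone as randomised gives 4.6% to 5.1%.
- Rare failure (about 1% at the early check): 4.6% to 5.5%.
- Worsening that persists across the valve change (42 patients): 4.8% to 5.1% with pairs dropped.
- Deviations that persist only within a period: dropping pairs still gives about 6% to 8%.
- Permanent change plus a decline of 1 point per visit (42 patients): bias with pairs dropped is -0.15 to +0.27, so it can go against the shunt.

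**The case against.** The strongest reply is that the plan already points to a sound analysis. Section 7c speaks of any patient, and section 4f records failure against whichever arm the patient was in, which suggests carry-forward in both arms. Differences are formed within each treatment-order group and follow-up data continue after failure, which suggests the week-12 score by randomised sequence. With that combination the error is about 5%. This stands as a plausible intention. But the added condition of being discontinued narrows the rule, no section discontinues a draining failure, and the optional paired t-test needs a non-draining score that this patient lacks.

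A second reply is that the high figures need extreme inputs. This also stands: treating the whole SD of 5 as visit noise is an upper limit, since that SD can include real differences in response. The assumed latent range also starts at or below the entry limit.

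Three stronger readings are tempting, and the documents do not support them.
- A reader might infer that the sponsor intended one-arm carry-forward. The text permits this but does not state it.
- A reader might fill the undelivered non-draining period with the failure score, which gives error up to about 31% with 42 patients. No passage does this.
- A reader might infer that a 5-point result could be produced by these rules alone. The bias is far smaller than that.

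**Conclusion.** The point holds as a gap in the analysis plan that should be fixed. That draining-first failures have no rule follows from the text alone. That carry-forward is one-sided is the literal reading, not a certain one.

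The size is conditional. At 34 evaluable patients, with transient scores and literal carry-forward, false-positive error is about 7% to 16% with pairs dropped and about 6% to 9% by sequence. Moderate visit noise belongs at the low end. Inflation is negligible if failures are rare, and near zero if worsening persists across the valve change. Persistence within a period alone does not remove it when pairs are dropped. The bias, at most about 0.9 points, does not threaten a true 5-point finding. What is at stake is false-positive control and a choice of handling made after the data are seen.

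Confidence in the size is medium. MCV Gait Grade, gait velocity, the Wilcoxon fallback and falls as a failure trigger were not modelled.

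**What to change.** In section 7c, analysis only:

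- (a) Apply one rule in both arms: the score at first failure within a period is that period's end score. State which score is used for a fall between visits.
- (b) Keep every randomised patient. Make the primary analysis by randomised sequence, using the week-12 score where the non-draining period was not delivered, and state that this dilutes a real effect.
- (c) As sensitivity analyses, report a mixed model on all available period scores with the undelivered score missing, scheduled scores without carry-forward, and the randomised period-1 comparison at week 6.
- (d) Fix these rules before any outcome data are analysed. Unblinding is not a usable milestone, because the neurosurgeon and neurologist are never blinded.

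**Cost.** Wording only, no new data. An observed week-6 score after an earlier failure is set aside. At a latent 2-point effect (42 patients, visit SD 3.5, failure at ≤18), power is 63.8% by sequence against 69.7% for the mixed model. Dropping pairs under literal carry-forward shows 91.1%, but that includes upward bias. At a 5-point effect every crossover version has about 100% power.

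**To reconcile separately**, because these texts decide who is affected:
- the failure cut-off: section 4a has "neurosurgeon remain informed about treatment failure (Tinetti Gait and evaluation <18", while section 4f uses ≤18;
- the six-week crossover in section 4a against the bar in section 4f;
- whether that bar covers patients who fail only by a fall;
- visit timing: every third week in section 4a; within 2 weeks and then 6, 9 and 12 weeks in section 4b.

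This review does not say which of these is right.
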